Title: Zonisamide Treatment of Alcohol Use Disorder: an Evaluation of Efficacy and Mechanism of Action

NCT #: NCT02900352

Document date: June 5, 2020

Document Type: Protocol and Statistical Analysis Plan

1. Principal Investigator: [name]., M.S.

2. Project Title:

"Zonisamide treatment of Alcohol Use Disorder: an evaluation of efficacy and mechanism of action"

3. Purpose, hypothesis and key questions

Purpose: To comprehensively evaluate the efficacy of an anticonvulsant medication zonisamide (ZNS) for the treatment of alcohol dependence in civilians. We want to see if the medication works to reduce harmful drinking patterns, and try to determine whether medication response can be predicted by a few key factors such as genotype, the age of onset of alcoholism (early vs. late), or stress-reactivity. This protocol also contains translational substudies that will help elucidate the mechanism of action of the medication and determine subject characteristics that predict preferential response.

SPECIFIC AIMS: Zonisamide (ZNS) is an anticonvulsant medication for which evidence of efficacy in treating alcohol use disorders (AUDs) was obtained in two small placebo-controlled pilot studies. We propose to 1) add a civilian arm (N=160) to complement the existing VA/CSR&D study comparing ZNS to placebo over 16 weeks of treatment; 2) add important mechanistic and translational components to both trials (potential N=320) to elucidate the mechanism of action of ZNS and enhance our understanding of how anticonvulsant treatments reduce drinking. Importantly, there is no overlap between the VA/CSR&D funding, and the proposed NIH funding. So we will evaluate *efficacy*, *safety*, *and mechanism of action* of zonisamide in treating alcoholism.

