AUDs are highly prevalent in civilians and in veterans, and the prevalence may be increasing over time, at least for civilians. ZNS is an extremely promising medicine for treating AUDs and managing other clinical problems including psychiatric disorders. ZNS is an affordable, generic anticonvulsant with unique actions on the major neurotransmitter systems

V.6 05Jun2020 4

involved in alcoholism, and it has neuroprotective effects. We completed a randomized, placebo-controlled pilot study of ZNS in treating AD that showed significant reductions in heavy drinking, overall drinking, and alcohol craving. ZNS was very well tolerated in this study. In this application, we propose a larger (N = 160), 16-week, randomized, double-blind, placebo-controlled, efficacy study of ZNS in reducing drinking and improving outcomes in a representative population of heavy-drinking civilians with AUD.

6. RESEARCH PLAN/EXPERIMENTAL METHODS:

6.A. CLINICAL TRIAL METHODS OVERVIEW: Overall trial design: ZNS treatment of civilians with AUD: The proposed study, which is registered on clinicaltrials.gov (NCT02900352), will be a two-arm, parallel-groups comparison of ZNS and PLC on outcomes of reducing and eliminating heavy drinking in subjects with AUD. We will conduct a 16 week, randomized, double-blind, placebo-controlled study in N=160 regularly heavy drinking subjects with DSM-5 AUD. We will enroll patients whose goal is to reduce their drinking to safe levels or to stop drinking. At each visit, all patients will receive Medical Management [47], which was developed for the COMBINE Trial and which we modified to be relevant for both reducing heavy drinking and promoting abstinence. Random assignment to treatment group and double-blind conditions will be maintained throughout the study. Raters will be trained in the reliable use of all assessments. We will use serum GGTP, Phosphatidyl Ethanol (PEth), Ethyl Glucuronide, and Ethyl Sulfate (EtS) to validate patient reports. Following a 1-2 week pre-treatment assessment period, patients will receive 16 weeks of treatment. Daily reports obtained using IVR will be used to identify subjective correlates of medication effects (e.g., craving) and to monitor medication use. A half-day long "stress response" laboratory session based on that developed by Sinha [48] will be performed with subjects after screening but before starting medication (baseline stress/impulsivity), and then a second lab will be performed between weeks 9-16.

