6.K.2 Secondary outcome measures: We will use a mixed models approach to examine for a statistically significant difference on heavy drinking days (HDD) per week, changes in GGTP level, measures of alcohol urge/craving (AUQ), and alcohol-related problems (as measured on the SIP). For each of these outcome measures, the model will include fixed effects for medication group, week, and the interaction between medication and week. We will include pre-treatment drinking behavior (past month HDD) as a covariate and will select the best-fitting variance-covariance structure based on Schwartz-Bayesian Information criterion (BIC). We will incorporate a grace period corresponding to the time it takes to titrate the medication to target dose into the models, and we will focus the primary analysis on the 8 weeks of treatment at the target dose. We will use the Hommel's correction for multiple comparisons on the secondary outcomes to guard against chance findings. With last secondary outcome measure percentage of subjects with no heavy drinking days (PSNHDD), we will use a logistic regression analysis with PSNHDD as a categorical dependent variable. Medication condition (PLC or ZNS) will be the main independent variable, and we will include the variables of civilian or veteran status. and sex as covariates. We will also examine the use of biomarkers (GGT, PEth) to verify and adjust subjective drinking data as these biomarkers can detect occult harmful drinking when a subject is not forthcoming.

6. K. 3. Dropouts and missing data: For the analysis of PSNHDD using logistic regression, all dropouts will be counted as relapsed. For all repeated measures analysis, we will use all V.6 05Jun2020

available data on individuals and thus dropouts provide data until the point of dropout. We will compare dropout patterns between groups and if there are concerns of informative dropout and/or informative intermittent missing data, we will use pattern mixture models [98] to perform sensitivity analyses to our main analyses. Adherence to the medication will be evaluated and controlled for in secondary analyses. We will evaluate and compare both medication conditions (PLC, ZNS) for percentage of prescribed pills taken.

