- 6. K. 4. To use telephone-based daily process data collection to elucidate the mechanism of action of ZNS as it relates to changes in craving, anxiety, self-efficacy, and genetic variation (Specific Aim 2, Exploratory Aim 1): Multilevel models will be used to evaluate the associations between craving, self-efficacy, anxiety, and daily drinking and how these associations vary as a function of medication group and GRPS. Similar to [name] et al. [79], we will focus on predicting nighttime drinking (i.e., drinks consumed after the early evening report), but here we will use psychological measures reported during the early evening in the daily survey. Nighttime drinking levels will be determined by subtracting the number of drinks consumed during the current day from the total number of drinks consumed for that day (reported the following day). We will follow the general analysis scheme used by [name] et al. [79], but will use mixed effects/multilevel models, rather than generalized estimating equations (GEE) models [99] because mixed models give unbiased estimates under less restrictive assumptions about missing data. We will examine the number of drinks consumed (using a Poisson model or negative binomial model if there is overdispersion). We will use the HGLM module of the HLM7 program, as it is more flexible for some of our models than PROC GLIMMIX in SAS. Analysis will focus on the last eight weeks of treatment, consistent with the analyses of outcomes in Aim 1. We will test the hypothesis that ZNS reduces nighttime drinking and that craving, anxiety, and GRPS act as moderators of this effect. We anticipate greater ZNS effect in subjects with greater anxiety, craving and genetic loading (greater GPRS). We will examine whether ZNS's effect on drinking is mediated by self-efficacy using the approach of Kraemer et al. [100, 101], such that self-efficacy is significantly affected by ZNS treatment, and has a main or interaction effect on nighttime drinking in the model containing both treatment and the potential mediator as predictors.
- 6. K. 5. Stress Reactivity Lab (Exploratory Aim 2): We will compare pre- and post-treatment changes in levels of anxiety, craving, and impulsivity measures induced by stressful and alcohol-cue imagery in the lab. We will test if the mean induced changes are attenuated by ZNS more than placebo using ANCOVA. The amount of reactivity pre-treatment will be explored as a covariate in secondary outcome models.

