- **6.K. 6. Safety:** Safety will be analyzed using categorical outcomes, defined by the type and severity of adverse effects. Summary measures of adverse events will be developed by organ system from the SAFTEE [77, 78] and will be compared for patients receiving ZNS or PLC using \Box^2 analysis or Fisher's exact tests, with an emphasis on moderate-to-severe adverse events.
- 6. K. 7. Sample Size And Power Estimate (Specific Aim 1): For continuous outcomes, based on the effect sizes from our pilot study of ZNS (showing a moderate effect size on drinks/week d=0.5, and .27 HDD/week), we estimated that a study with N=128 subjects (a 20% drop out rate) would be well powered (>.80) to detect a medium effect size difference on the secondary outcomes HDD per week and total drinks per week for the main effect of group assuming alpha level of 0.05. Based on past trials we are expecting a dropout rate < 30%. We will quantitatively examine the veteran and civilian populations for differences in variance and treatment response, and combine them (if valid) in a patient-level pooled analysis, further increasing power on all outcomes. If substantial differences are observed between the veteran and civilian samples, we will meta-analyze them. For PSNHDD, from the pilot study, in the ZNS group, 12 of 20 subjects did not relapse in the 28 days of the study, compared to 7 of 20 PLC subjects. Using this effect size, the proposed sample size of 80 subjects per group has >89% power to detect such a difference in the rates of no heavy drinking (i.e. 60% vs. 35%), assuming a two-sided alpha level of 0.05. We can also detect slightly smaller differences (60% vs. 38%, 35% vs. 57%) with 80% power under the same assumptions. Both in the estimation of effect

size from the pilot data and in the sample size analysis, dropouts are counted as relapsed to heavy drinking.

6 K. 8. Pharmacogenomic and Micro-longitudinal analyses power estimate (Aim 2, exploratory aims): There is little ZNS-specific data by which we could reasonably estimate effect sizes for these analyses. Three recent treatment studies by our group showed significant pharmacogenetic effects with samples of about 110-150 in each [15, 85, 102]. By using a mixed models approach on drinking variables, and HLM for the micro-longitudinal analyses, we will be adequately powered to detect medium-to-large effects in these analyses.

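### The PSNHDD logistic model omits past-month HDD, which every other primary and secondary efficacy model includes, and lists a civilian/veteran covariate that varies only in the pooled analysis

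*Combined protocol and SAP*

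**What the plan says.** **PSNHDD model (6.K.2).** The plan states that "we will use a logistic regression analysis with PSNHDD as a categorical dependent variable". Medication condition is the main predictor, and "we will include the variables of civilian or veteran status. and sex as covariates". No measure of baseline drinking is named.

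**Other primary and secondary efficacy models (6.K.1.a and 6.K.2).** The same sentence appears for the primary outcome, drinks per week, and for the four continuous secondary outcomes (HDD per week, GGTP, AUQ craving, SIP problems): "We will include pre-treatment drinking behavior (past month HDD) as a covariate". None of these models carries a civilian/veteran term.

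**Population.** Section 3 proposes to "add a civilian arm (N=160) to complement the existing VA/CSR&D study comparing ZNS to placebo", and section 5 describes a study "in a representative population of heavy-drinking civilians with AUD". Under 6.B, veterans may be enrolled at VCU IDAS for the translational components only.

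**Power (6.K.7).** For 60% vs 35%, "the proposed sample size of 80 subjects per group has >89% power". The same section plans to combine civilians and veterans at patient level if that proves valid, and otherwise to meta-analyze the two studies. Dropouts count as relapsed (6.K.3, 6.K.7), so all 80 per group enter the PSNHDD analysis.

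**The concern.** PSNHDD is defined by heavy drinking days, so baseline heavy drinking is the natural covariate for it. It is nevertheless the one primary or secondary efficacy outcome whose model leaves baseline heavy drinking out. One of the two covariates that are listed cannot vary in the population for which the outcome is powered.

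Two things are at stake. First, 6.K.2 does not say which analysis set the covariate list serves, so a reader cannot tell whether the pre-specified PSNHDD analysis is the civilian trial or the pooled data. Second, the civilian analysis reduces to medication plus sex. That gives up whatever precision baseline HDD would bring. It also leaves any chance imbalance to be handled after the data are seen, since randomization is stratified on site and antidepressant/psychotropic use (6.E.4) and not on baseline drinking.

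**Working it through.** **1. The plan's own power figure.** Inputs from 6.K.7: n = 80 per group, two-sided alpha 0.05. Unadjusted two-proportion formula with pooled variance under the null:

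power = Φ[(d − 1.96·SE0) / SE1], with SE0 = √(2·p̄(1−p̄)/n) and SE1 = √((p1(1−p1) + p2(1−p2))/n).

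- 60% vs 35%: d = 0.25, p̄ = 0.475, SE0 = √(0.49875/80) = 0.0790, SE1 = √(0.4675/80) = 0.0764. Then (0.25 − 0.1548)/0.0764 = 1.246, so power is 89.4%. The stated figure of more than 89% reproduces.
- 60% vs 38%: 80.1%. 35% vs 57%: 80.3%. Both reproduce the stated 80%.

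This calculation contains no covariates, so the stated power does not depend on the covariate list.

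**2. Can the civilian/veteran term be estimated?** Take the design matrix with columns for intercept, medication, civilian/veteran status and sex.

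- Civilians only (N = 160): the status column is the same for everyone and is therefore a multiple of the intercept. Rank is 3 with 4 columns, so the coefficient cannot be estimated. Removing it leaves the medication estimate unchanged.
- Civilians and veterans pooled (N = 320): rank is 4 with 4 columns, so it can be estimated.
- Separate studies combined by meta-analysis: the term is constant within each study, as in the first case.

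**3. What past-month HDD would add.** The documents give no association between baseline HDD and PSNHDD, so a range is assumed. Model: logit P(no heavy drinking days) = a(arm) − ln(OR)·x, with x standard normal and a(arm) solved so that the marginal rates stay at the planned values. There are 80 per arm and 6,000 trials per setting. The test is a Wald test of medication at two-sided 0.05, with sex in both models. The Monte Carlo standard error of one power estimate near 90% is √(0.9·0.1/6000), about 0.4 points.

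Two separate runs at 60% vs 35%:

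| Assumed OR per SD of HDD | Run 1: sex only → with HDD | Run 2: sex only → with HDD |
|---|---|---|
| 1.0 | not run | 0.895 → 0.893 |
| 1.5 | 0.893 → 0.904 | 0.893 → 0.902 |
| 2.0 | 0.892 → 0.917 | 0.898 → 0.924 |
| 2.5 | 0.889 → 0.929 | 0.888 → 0.927 |
| 3.0 | not run | 0.894 → 0.946 |

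The gains at 1.5, 2.0 and 2.5 are 1.1, 2.5 and 4.0 points in run 1 and 1.0, 2.6 and 3.9 points in run 2. They are nil at 1.0 and 5.2 points at 3.0. The sex-only results agree with the closed-form 89.4%.

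At 60% vs 38%, in one run: 0.812 → 0.824, 0.794 → 0.832 and 0.798 → 0.858 for odds ratios of 1.5, 2.0 and 2.5. These are gains of 1.2, 3.8 and 6.0 points.

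**4. Effect on the estimand.** The unadjusted odds ratio at 60% vs 35% is (0.60/0.40)/(0.35/0.65) = 2.79. With the marginal rates held fixed, the odds ratio conditional on HDD is 2.90, 3.11 or 3.34 at the three assumed strengths.

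**The case against.** The strongest defence is that the civilian/veteran term belongs to the pooled analysis. Section 6.K.7 plans that analysis openly and for all outcomes, and 6.K.1.a also anticipates combining the samples. In the pooled data the covariate varies and is appropriate. This stands, and it rules out reading 6.K.2 as a concealed switch to pooled data. It does not settle the text: pooling is conditional, 6.K.2 does not tie the PSNHDD model to it, and the stated power is for 80 per group.

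A reader might infer that the model cannot be fitted. In practice the constant term would be dropped with no effect on the medication estimate, so no result is lost.

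A reader might infer that PSNHDD is the only model in the plan without baseline HDD. The documents do not support that. The Aim 2 models examine "how these associations vary as a function of medication group and GRPS", the stress-lab analysis says "We will test if the mean induced changes are attenuated by ZNS more than placebo using ANCOVA", and neither states baseline HDD; nor do the safety comparisons in 6.K.6. The contrast holds for the primary and secondary efficacy models only.

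On the missing covariate, randomization makes the comparison of medication plus sex valid without it, and 6.K.1.a makes identifying baseline differences an initial step. Both points stand, but identifying a difference is not a commitment to adjust for it. It is also fair that the gain is small and rests on an assumption, and that the entry requirement of at least 2 heavy drinking days per week (6.C) narrows the range of HDD and may weaken its predictive strength.

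The randomization strata are not listed in the PSNHDD model either. That is true of the other efficacy models too, and is a separate matter.

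**Conclusion.** The point holds as a modest specification gap in one secondary outcome. The PSNHDD model omits a baseline covariate that the primary model and all four continuous secondary models use. One of its two listed covariates has no role in the civilian analysis on which the power rests.

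The cost at 60% vs 35% is about 1 to 4 power points for assumed odds ratios of 1.5 to 2.5 per SD, and near zero if HDD predicts weakly. There is also no pre-specified adjustment for chance imbalance in baseline heavy drinking. The documents do not support a stronger conclusion that the treatment comparison is biased or that the stated power is wrong: the omission costs precision only, and the unadjusted figure reproduces.

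The sizes assume a normally distributed covariate, sex unrelated to outcome, and testing at 0.05 as in 6.K.7, not at a Hommel-adjusted level. That the efficacy sample is all civilian rests on the trial description; the listed eligibility criteria do not themselves exclude veterans.

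**What to change.** In 6.K.2, state two PSNHDD models:

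- **Civilian trial:** logistic regression on medication, past-month HDD and sex.
- **Pooled civilian-plus-veteran analysis, if carried out under 6.K.7:** the same model plus civilian/veteran status.

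This takes a sentence or two in the SAP and no new data, since the 90-day timeline follow-back at screening (6.E.1) already covers past-month HDD. The small downside is that the reported odds ratio becomes conditional on baseline HDD and is expected to lie somewhat further from 1 than the unadjusted one. The text should say so, and the raw proportions by arm can be shown beside it.

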The target dosage for ZNS is 500mg/day, which will be titrated up over the first 7 weeks of treatment, with dosage increases based on tolerability. The titration schedule will start with 100mg daily, increased to 200mg/day after the first week, and then increased by 100mg/day every 2 weeks to the target dose of 500mg/day. Subjects will then begin 9 weeks at the target dose with the option to increase to 600mg daily after two weeks at target if treatment response is suboptimal and there are no significant side effects (no current moderate to severe AE's with 500mg daily, which will be assessed at visits as described in Section 6.F.2 "Counseling"). Dosing will remain flexible with respect to the time of day that the medication is administered, in order to maximize compliance and minimize the impact of adverse effects. The dosage will be held or reduced based on the appearance of moderate-to-severe adverse effects. Following the seven week titration phase, subjects will begin the 9 week period of active treatment on the target dose, followed by up to 2 weeks of tapering and discontinuation of the medicine, and a return for follow-up at three months post-treatment. The dosing is also flexible in that it will allow subjects to continue on at less than the target dose based on tolerability, but subjects must be able to tolerate at least 200mg/day (two pills). Also, if subjects are not having moderate to severe side effects during the treatment phase, and have not yet reached 600mg/day, they may be increased by up to 100mg every 2 weeks if it is felt that they may benefit further from it. This will allow maximum flexibility and optimal dosing.

6.B. Subjects and recruitment: The clinical trial portion of this study is being conducted at two sites; (1) VCU's Institute for Drug and Alcohol Studies (IDAS) and (2) the University of Connecticut Health Center (UCHC) in Farmington CT, which also has its own NIAAA-funded Alcohol Research Center. This Project will benefit from the expertise and resources for conducting clinical trials at both centers. Both sites recruit from different catchment areas and have good records of subject recruitment. N= 160 subjects will be randomly assigned to receive

V.6 05Jun2020 5

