trial is summed. 5) Visual learning and memory: The Brown Location Test (BLT) is a visual learning task independent of verbal, global intellectual, fine motor or drawing skills that consists of five recall learning trials, an interference trial, and a short delay recall. In this task, presented on a computer screen, subjects are shown a series of 12 images for 4 seconds each that contain one red dot in different locations on a common field of 56 non-symmetrically placed circles. Subjects are then presented a page with the 56 non-symmetrically placed circles and instructed to place 12 red dots at the positions in which they appeared in the prior presentations. Following five red dot learning trials an interference trial is presented using one trial of 12 images with black dots in different locations on the circle array and asked to indicate the locations of the black dots. A final blank 56 circle array is provided and subjects asked to indicate the positions of the red dots learned in trials 1-5. Total correct for trials 1-5 sum, interference and delayed recall are scored. Normative data are available for each of these neuropsychological tasks[72-76].

- *g. Medication adverse effects:* Patients will provide subjective reports of side effects at each study visit using the Systematic Assessment for Treatment Emergent Effects (SAFTEE) interview [77], a widely used measure of adverse events. A standardized approach was developed for use in alcohol treatment trials [78].
- **h. Measures of treatment received:** Records of medication taken will be kept and patients will be asked to return the unused portion of study medication at each visit. The nurse will also record the number of contact hours patients have been exposed to any alcohol treatment outside of the study.

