- **6.K.1. Procedures:** Procedures for the monitoring and analysis of data were developed during previous clinical trials conducted at Yale and will be overseen by Drs. [name] and [name].
- 6.K.1.a. To Examine the Efficacy of ZNS (Specific Aim 1), Primary Outcome: We will use *drinks per week* as the primary outcome variable. This is also the primary outcome we are using for veteran ZNS study, and is one that can be readily applied when combining the samples. Recently the NIAAA and FDA Alcohol Clinical Trials Initiative (ACTIVE: a workgroup of experts in the field tasked with optimizing alcoholism clinical trials outcomes and methods) has suggested that for medication development trials and small to medium size trials, continuous outcome variables such as drinks/week or heavy drinking days per week are optimal as opposed to categorical outcomes. We will use a mixed models approach to examine for a statistically significant difference in drinks per week and on continuous secondary outcome variables. The model will include fixed effects for medication group, week, and the interaction between medication and week. We will include pre-treatment drinking behavior (past month HDD) as a covariate and will select the best-fitting variance-covariance structure based on Schwartz-Bayesian Information criterion (BIC). We will incorporate a grace period corresponding to the time it takes to titrate the medication to target dose into the models, and we will focus the primary analysis on the last 8 weeks of treatment at the target dose. All of these outcomes can be obtained from the TLFB data, and from the daily drinking data obtained from the IVR.

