An important initial consideration in considering efficacy will be to identify baseline differences between groups that may have occurred despite randomization. A successful outcome during the treatment trial will be defined in terms of a statistically significant difference on the primary outcome measure: drinks per week, compared during the 8 weeks of active treatment at the target dose, allowing for an 8 week grace period for the medication titration. For all analyses, heavy drinking days will be defined as follows; for men > 4 drinks in a day and for women > 3 drinks in a day. Patients will be followed irrespective of whether they continue to receive medication treatment, so that analysis will include all data available for the 8-week treatment period. All analyses will be **intent-to-treat**. The α will be set at .05 for the primary outcome variable. Between site differences will be explored. We will test interaction effects of GRPS in the regression models for the primary/secondary outcomes (**Exploratory Aim 1**), testing the hypothesis that ZNS's effect on drinking is greater in those with higher GRPS.

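### Section 6.K.3 adjusts secondary analyses for adherence, which is measured after randomisation; that comparison loses the protection of randomisation and does not fit the plan's intent-to-treat rule

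*Combined protocol and SAP*

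**What the plan says.** Section 6.K.3 (Dropouts and missing data) commits to the adjustment: "Adherence to the medication will be evaluated and controlled for in secondary analyses". The next sentence names the measure: "We will evaluate and compare both medication conditions (PLC, ZNS) for percentage of prescribed pills taken". The data come from pill returns (6.G.5.h: "patients will be asked to return the unused portion of study medication at each visit") and from daily telephone self-report of medication use (6.G.6.c). Both are collected during treatment.

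Section 6.K.1.a sets the general rule: "All analyses will be intent-to-treat". It adds: "Patients will be followed irrespective of whether they continue to receive medication treatment". The primary model there has no adherence term: "The model will include fixed effects for medication group, week, and the interaction between medication and week". Its one named covariate is measured before treatment: "We will include pre-treatment drinking behavior (past month HDD) as a covariate". Section 6.K.2 lists the model terms for the secondary outcomes, and adherence is not among them.

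The plan does not say which secondary analyses are meant, how adherence enters the model, what quantity is being estimated, or how the result will be labelled.

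**The concern.** Randomisation balances the arms on what exists at baseline. Pill-taking happens later, and assignment can change it. Section 4.A.1 calls side effects a barrier to using medications for alcohol use disorder, and 4.A.2.b reports some cognitive side effects of zonisamide. The plan itself intends to compare adherence between the arms.

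Adherence also plausibly goes with motivation, and so with drinking. Holding it constant sets zonisamide patients beside placebo patients with the same pill percentage. If zonisamide is harder to take, those who reach that percentage on zonisamide are not the same kind of patient as those who reach it on placebo. The adjusted difference is then neither the intent-to-treat effect nor the effect of taking the drug. At stake is an adherence-adjusted result reported beside the main one that shows a difference the drug did not cause, or hides one that it did.

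**Working it through.** **1. What the plan's figures give.** There is no planning figure for adherence: no expected level, no difference between arms and no correlation with drinking. The relevant stated figure is the planning effect in 6.K.7, d = 0.5 on drinks per week with N = 128, power above 0.80. With 64 per arm I get 0.807 (normal) and 0.801 (noncentral t), so it reproduces, and 128/(1 - 0.20) = 160. It does not depend on the adherence question; I use d = 0.5 only as a yardstick.

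**2. Inputs.**
- From the documents: 80 per arm (Specific Aim 1); alpha 0.05 for the primary outcome (6.K.1.a).
- From the documents, extended: two-sided testing, which 6.K.7 states for the outcome of no heavy drinking days and which I apply here.
- Assumed: the within-arm correlation r between adherence and drinking, -0.1 to -0.5, produced by an unmeasured factor that drives both.
- Assumed: the difference D in mean adherence, zonisamide minus placebo, in within-arm SD units, from -0.5 to +0.25.
- Assumed: adherence enters as a linear covariate, and the true zonisamide effect is zero.

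**3. Bias.** Adjusted effect = intent-to-treat effect - b × D, where b is the within-arm slope of drinking on adherence. In SD units b = r. With no true effect, the adjusted effect is -r × D, and a negative value means less drinking on zonisamide.
- r = -0.1, D = -0.25: -(-0.1)(-0.25) = -0.025 SD
- r = -0.3, D = -0.5: -(-0.3)(-0.5) = -0.15 SD
- r = -0.5, D = -0.5: -(-0.5)(-0.5) = -0.25 SD
- D = 0: no bias at any r
- D = +0.25, r from -0.1 to -0.5: +0.025 to +0.125 SD, against zonisamide

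**4. Type I error, approximate.** SE = sqrt(1 - r²) × sqrt(2/n + D²/(2n - 2)). For r = -0.3, D = -0.5, n = 80: sqrt(0.91) × sqrt(0.025 + 0.25/158) = 0.1555. Bias/SE = 0.15/0.1555 = 0.964. Rejection probability = Φ(0.964 - 1.96) + Φ(-0.964 - 1.96) = 0.161.

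**5. Simulation.** 20,000 trials per setting, no true effect, 80 per arm, two-sided rejection rate with adherence as a covariate:

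| r | D = -0.25 | D = -0.5 |
|---|---|---|
| -0.1 | 0.052 | 0.061 |
| -0.2 | 0.062 | 0.095 |
| -0.3 | 0.078 | 0.160 |
| -0.4 | 0.106 | 0.266 |
| -0.5 | 0.149 | 0.422 |

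The middle case (0.160) agrees with step 4, and 0.158 of it favours zonisamide. With D = 0 the rate is about 0.05. With D = +0.25 it is 0.054 to 0.147, and the excess goes against zonisamide. With 64 per arm and D = -0.5 it is 0.058 to 0.352. Leaving adherence out gives about 0.05 in every setting.

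**6. Scale.** Against d = 0.5, the biases toward zonisamide are 0.025/0.5 = 5%, 0.15/0.5 = 30% and 0.25/0.5 = 50% of the effect the trial was planned to find.

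**The case against.** The strongest reply is that this is a supplementary analysis beside an intact intent-to-treat result. That largely stands. A reader might infer that the trial's main randomised comparison is broken. It is not: the primary model contains no adherence term, success is defined on the primary outcome alone, and patients are followed on or off drug.

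A reader might also infer that adherence enters the Hommel-corrected secondary outcome tests. The text does not establish that. Section 6.K.2 lists those models without adherence, and the sentence in 6.K.3 directly follows a passage on sensitivity analyses. The wording is not conclusive, so it needs clarifying.

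A third tempting reading is that the adjustment will manufacture a zonisamide benefit. That is one direction of several. The documents describe zonisamide as well tolerated (4.A.2.b, section 5), dosing bends to tolerability (6.A, 6.F.1), and both arms receive counselling that supports adherence (6.F.2). The difference between arms may be small. At 0.25 SD lower adherence and correlations of -0.1 to -0.2, the type I error is only 0.052 to 0.062. None of this shows that adherence will equal placebo, however, and the analysis is safe only if it does or if adherence is unrelated to drinking.

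Finally, one might cite the rule in 6.A, "The dosage will be held or reduced based on the appearance of moderate-to-severe adverse effects", as a route by which the arms diverge. It does not serve. The measure is a percentage of what was prescribed, so a directed hold or reduction need not lower it; missed pills or stopping would.

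**Conclusion.** The point holds for the secondary analyses only. The sentence in 6.K.3 commits to conditioning on a variable measured after randomisation, and such a comparison cannot be reconciled with the statement that all analyses are intent-to-treat. The primary test and the power figures are untouched.

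The size cannot be fixed from the documents. Over the assumed range with lower zonisamide adherence, it runs from negligible to serious. The 42% figure is the extreme corner of that range, not an expectation. All the figures rest on the assumed r and D, on linear covariate entry, and on a common cause of adherence and drinking. The defect itself does not rest on those values: the adjusted comparison has no randomisation behind it, whichever way the bias runs. This should be corrected, and the correction is cheap.

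**What to change.** In 6.K.3, delete the commitment to control for adherence, so that adherence is evaluated only. State that no test of a primary or secondary outcome includes adherence as a covariate. Keep the comparison of pill percentage by arm, as a descriptive report. This also settles what the phrase about secondary analyses means and removes the conflict with the intent-to-treat rule.

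If an on-drug effect is wanted, pre-specify a complier-average estimate, label it exploratory, and use randomised arm as the instrument for active zonisamide taken, set to zero for everyone on placebo. The exposure must be defined this way. Pill returns and telephone reports count capsules in both arms, so an instrument for capsules taken would rest on a difference between arms that could be near zero or negative, and the estimate could be unstable or reversed. State the exclusion restriction: assignment affects drinking only through zonisamide actually taken.

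The cost is wording. The data are already being collected, and sample size, visits and the primary analysis do not change. The downside is that the instrumental-variable estimate will have a wider interval than the covariate-adjusted one.
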